10.3.1.2 Ordering of Laboratory Parameters

The tables and listings, parameters are presented in the following order ([Section 12.1](#)):

- **Hematology**

Quantitative data: Red Blood Cell (RBC, also called erythrocytes) count, hemoglobin, hematocrit, platelets, White Blood Cell (WBC, also called leukocytes) count, differential blood count, (basophil, eosinophil, neutrophil, lymphocyte, monocyte), reticulocyte count, MCV, MCH, and MCHC

- **Blood chemistry**

Quantitative data: AST, ALT, GGT, ALP, Total bilirubin, Creatinine, Creatinine clearance, Sodium, Potassium, Calcium, Total protein, and Albumin, BUN,,

10.3.2 Tables

A table Hematology Observed Values and Changes from Baseline presents for subjects on adjunctive therapy and for subjects on monotherapy, separately per analysis visit summary statistics:

- For absolute values

- For Change from Baseline values.

This by visit presentation includes scheduled visits and Last Visit.

The table is repeated for:

- Blood Chemistry Observed Values and Changes from Baseline values.

A table Hematology: Shift from Baseline to End of Treatment presents for subjects on adjunctive therapy and for subjects on monotherapy, separately the number of shifts from:

- “Low” at Baseline and “Low” at End of Treatment
- “Low” at Baseline and “Normal” at End of Treatment
- “Low” at Baseline to “High” at End of Treatment
- “Normal” at Baseline to “Low” at End of Treatment
- “Normal” at Baseline to “Normal” at End of Treatment
- “Normal” at Baseline to “High” at End of Treatment
- “High” at Baseline to “High” at End of Treatment
- “High” at Baseline to “Normal” at End of Treatment
- “High” at Baseline to “Low” at End of Treatment

The table is repeated for:

- Blood Chemistry.

A table Treatment-emergent PCS Hematology by Analysis Visit presents the number and percentage of subjects with treatment-emergent PCS criteria (Too low, Too high) for each of the respective parameters. Tables will be presented for subjects on adjunctive therapy and for subjects on monotherapy, separately.

Note: Category “Not PCS” is omitted due to limited usefulness.

Frequencies are presented as:

- n over Nobs with n being the number of subjects with PCS criterion for the respective variable at least at one visit during that period and Nobs being the number of subjects with at least 1 non-missing measurement for respective variable during that period.
- Percentage (%) based on Nobs

The table is repeated for:

- Blood Chemistry PCS Data.

A table Hematology PCS Shift from Baseline presents, for each period and for the combined periods changes from Baseline in the PCS abnormality category at any time during the respective period and overall. Tables will be presented for subjects on adjunctive therapy and for subjects on monotherapy, separately.

The table presents the following settings:

- “Too low” at Baseline and “Too low” at least at one visit during that period
- Shifts from “Too low” at Baseline to “Too high” at least at one visit during that period
- Shifts from “Not PCS” at Baseline to “Too low” at least at one visit during that period
- Shifts from “Not PCS” at Baseline to “Too high” at least at one visit during that period
- “Too high” at Baseline and “Too high” at least at one visit during that period
- Shifts from “Too high” at Baseline to “Too low” at least at one visit during that period
- “Too low”, “Not PCS”, and “Too high” at Baseline for those subjects having at least one measurement during that period.

Note: Shifts to status “No PCS” are omitted due to limited usefulness.

Frequencies are presented as:

- n over Nobs with n being the number of subjects with at least one measurement during that period meeting the criteria for the respective variable and Nobs being the number of subjects with at least one non-missing measurement for the respective variable during that period and at baseline.

- Percentage (%) based on Nobs

For this table a subject can appear in more than one shift.

The table is repeated for:

- Blood Chemistry PCS Shifts.

A table Potential Drug Induced Liver Injury (PDILI) Data presents for subjects on adjunctive therapy and for subjects on monotherapy, separately, the number and percentage of subjects with the following criteria:

- ALT or AST $\geq 5\times$ ULN
- ALT or AST $\geq 3\times$ ULN and coexisting total bilirubin $\geq 2\times$ ULN

Frequencies are presented as:

- n over Nobs with n being the number of subjects with at least one measurement during that period meeting the criteria for the respective variable and Nobs being the number of subjects with at least one non-missing measurement for the respective variable during that period and at baseline.
- Percentage (%) based on Nobs

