5.1.5 Planned number of subjects and sites

The planned number of evaluable subjects in the First Period will be a total of 38 subjects for the primary efficacy analysis. Subjects will be enrolled into 4 age groups (1 month to <6 months, 6 months to <1 year, 1 year to <2 years, and 2 years to <4 years), with a minimum of 5 subjects in each age group.

The planned number of monotherapy subjects will be a total of 10 subjects.

It is planned to have those subjects recruited in approximately 20 sites.

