10.3.1.1 Blood Sample

Blood samples are analyzed by a central laboratory and data are available electronically including SI units as well as an assessment of abnormality based on normal ranges (eg, high, low; adjusted for age and gender where applicable).

Change from Baseline (see [Section 3.3](#)) is calculated for each post Baseline visit according to the visit schedule including unscheduled visits and for the Last Visit.

A variable representing categories for possibly clinically significant treatment-emergent (PCST) abnormal values is created for selected hematology and blood chemistry parameters ([Table 12-1](#) and [Table 12-2](#)):

- Too low
- Not PCS
- Too high

PCST abnormal values are defined as any treatment emergent laboratory values meeting the criteria (UCB 2012, GUIDANCE DOCUMENT, Clinical and Laboratory Possibly Clinically Significant Treatment Emergent (PCST) Criteria For Clinical Development Programs in TA CNS).

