12.3.2 Chemistry**Table 12-2: PCST values for Chemistry**

Parameter	Age range	Unit (conventional)	Abnormality Criteria (conventional)	Unit	Abnormality Criteria (standard)
AST	<14 years	U/L	> 180	U/L	> 180
ALT	<1 year	U/L	\$	U/L	\$
	1 yr - <18 y		> 90		> 90
GGT	<6 month	U/L	> 522	U/L	> 522
	6 m - <1 y		> 279		> 279
	1 y - < 13 y		> 66		> 66
Alkaline Phosphatase	<4 year	U/L	> 690	U/L	> 690
	4 y - <10 y		> 834		> 834
Total Bilirubin	> 1 month	mg/dl	≥ 1.5	μmol/L	≥ 25.656
BUN	<1 year	mg/dl	> 21	mmol/L	> 7.497
	≥1 year		> 30		> 10.71
Creatinine	<1 year	mg/dL	\$	μmol/L	\$
	1 y - <10 y		> 0.9		> 79.56
Creatinine Clearance [#]	All	ml/min	≤ 70	mL/s	< 1.169
Sodium	> 1 month	mEq/L	≤ 130	mmol/L	≤ 130
			≥ 150		≥ 150
Potassium	< 1 year	mEq/L	< 3.0	mEq/L	< 3.0
			> 6.5		> 6.5
	≥ 1 year		< 3.0		< 3.0
			> 5.8		> 5.8
Calcium	< 1 year	mg/dL	< 6.9	mmol/L	< 1.725
			> 12.2		> 3.05
	1 y - <18 y		< 7.4		< 1.85
			> 11.7		> 2.925
Total Protein	<2 months	g/dL	\$	g/L	\$
	2 m - <1 yr		< 3.0		< 30
			> 10.0		> 100
	≥1 year		< 4.3		< 43
			> 10.0		> 100
Albumin	<1 year	g/dL	< 1.6	g/L	< 16
			> 6.0		> 60
	≥1 year		< 2.4		< 24
			> 7.0		> 70

Abbreviations: ALT= alanine aminotransferase; AST = aspartate aminotransferase; GGT: gamma-glutamyl transferase; BUN = blood urea nitrogen; dL = deciliter; L = liter; mg = milligram; mmol = millimoles; μmol = micromoles; U = unit; m=month (a month is defined as 30 days); y = years (a year is defined as 365.25 days)

^{\$} Not presented in reference [2]

[#] Schwartz equation (patients <12): Cr Cl ml/min = [Height (cm) * 0.55] / serum creatinine

Cockcroft equation (patients ≥12): Male: Cr Cl ml/min = [(140-age) x body weight (kg)] / (72 x serum creatinine); Female: Cr Cl ml/min = [(140-age) x body weight (kg)] / (72 x serum creatinine)] x 0.85

Note: The adjusted age ([Section 3.2.5.2](#)) at the assessment/visit will be used to determine within which percentile the subject is included.

This document cannot be used to support any marketing authorization application and any extensions or variations thereof.
PUBLIC COPY

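### In the PCS chemistry tables, infants with no ALT or creatinine criterion stay in the denominator, so those percentages are biased low at early visits

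*SAP*

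**What the plan says.** SAP 10.3.2 plans a treatment-emergent PCS table for hematology and repeats it for blood chemistry. The numerator is the number of subjects meeting the criterion. The denominator is "Nobs being the number of subjects with at least 1 non-missing measurement for respective variable during that period", and the table gives "Percentage (%) based on Nobs". The PCS shift tables use a similar base: "Nobs being the number of subjects with at least one non-missing measurement for the respective variable during that period and at baseline". Neither rule requires that a criterion exist at the child's age.

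Table 12-2 (SAP 12.3.2) supplies the chemistry criteria. For ALT and creatinine it has entries only from 1 year (above 90 U/L and above 0.9 mg/dL). The rows below 1 year, and the total protein row below 2 months, carry a footnote that the sponsor's guidance document gives no value. The table's closing note says that adjusted age "at the assessment/visit will be used to determine within which percentile the subject is included".

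SAP 10.3.1.1 allows three PCS levels (too low, not PCS, too high), with none for a value that cannot be classified. SAP 10.3.1 gives a different base for by-period laboratory tables: subjects who entered the period, within age category.

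Two of the four enrolment age groups lie below 1 year, "with a minimum of 5 subjects in each age group" (Protocol 5.1.5).

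**The concern.** A percentage of children with an abnormal value should be based on children in whom an abnormal value could be recognised. Under the stated rule, an infant with an ALT or creatinine result but no criterion adds to Nobs and can add nothing to the count. The printed percentage is then too low, by an amount that depends on the share of infants at that visit. AST has a criterion for everyone under 14 years, so the AST and ALT percentages in one table would describe different assessable groups without saying so.

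There is a related problem at baseline. SAP 10.3 calls a PCS value treatment-emergent if it was not observed during the Baseline period. An infant with ALT above 90 U/L at baseline has no criterion at that age. The same value after the first birthday is flagged and would count as treatment-emergent, although nothing has changed. The PCS shift table has no category for a baseline that cannot be classified.

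Laboratory tests are listed as other safety variables, and no hypothesis test is involved. At stake is the accuracy of a descriptive safety table for the youngest children in the trial.

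**Working it through.** The plan states no PCS incidence, so there is no figure to reproduce. The check has two parts.

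**1. Size of the dilution**

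Inputs:
- 38 subjects planned for the primary (adjunctive) efficacy analysis (Protocol 5.1.5, SAP 2.3). Tables are separate by therapy.
- Two age groups below 1 year with at least 5 children each, so 5 + 5 = 10 if the minimum applies within the 38.

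Assumptions: all 38 are measured, the infants are still under 1 year, and the 2 flagged children are an arbitrary illustration.

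Formulae: reported percentage = n / Nobs. Percentage among classifiable children = n / (Nobs − infants without a criterion).

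| Infants under 1 year among 38 | Classifiable | As the SAP defines it (n = 2) | Among classifiable | Ratio |
|---|---|---|---|---|
| 5 | 33 | 2/38 = 5.3% | 2/33 = 6.1% | 38/33 = 1.15 |
| 10 | 28 | 5.3% | 2/28 = 7.1% | 38/28 = 1.36 |
| 14 | 24 | 5.3% | 2/24 = 8.3% | 38/24 = 1.58 |
| 19 | 19 | 5.3% | 2/19 = 10.5% | 38/19 = 2.00 |

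With 10 infants, 10/38 = 26% of the denominator cannot be flagged, and the printed figure is 28/38 = 0.74 of the rate among classifiable children. SAP 3.1 anticipates few children in the two youngest groups, so the upper rows of the table are the more plausible ones.

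**2. How long it lasts**

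Age at assessment selects the criterion, so infants become classifiable on reaching 1 year (365.25 days in the Table 12-2 key; SAP 3.2.5.2 uses chronological age from 12 months). A child is classifiable at a visit on Day d if age at first dose is at least (365.25 − (d − 1)) / 30.4375 months. Target days are from SAP Table 3-1.

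| Visit | Day | Minimum age at first dose (months) |
|---|---|---|
| 4 | 15 | 351.25/30.4375 = 11.5 |
| 6 | 43 | 323.25/30.4375 = 10.6 |
| 10 | 99 | 267.25/30.4375 = 8.8 |
| 13 | 183 | 183.25/30.4375 = 6.0 |
| 15 | 267 | 99.25/30.4375 = 3.3 |
| 16 | 351 | 15.25/30.4375 = 0.5 |

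Even on the earliest day of the Visit 16 window (Day 337) the minimum is 29.25/30.4375 = 0.96 months, below the entry age of 1 month. The dilution is therefore nearly complete through Visit 6, weaker by Visit 13, and gone by about Week 50 for infants still on study.

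**The case against.** Three stronger readings are tempting, and the documents do not support them.

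- *Infants can never be flagged.* This holds only while the child is below the age limit. The Table 12-2 note uses age at the assessment, so infants who stay in the Second Period become classifiable.
- *Infant liver or renal abnormalities go unseen, or infants are displayed as assessed and normal.* Table 12-2 has criteria below 1 year for AST, GGT and BUN, and one for creatinine clearance at all ages. The low/normal/high shift tables use central-laboratory ranges "adjusted for age and gender where applicable". The PDILI table works on ULN multiples with no age limit. SAP 10.3 also lists every subject meeting a criterion of Appendix 12.3.3, and the listings show results with normal ranges. The by-visit PCS table omits the not-PCS category, so it prints nobody as normal.
- *The gap calls for a new ALT threshold in infants.* The blank cells are inherited from the sponsor's guidance document. In SAP 10.3.2 and Appendix 12.3.3, three times ULN is used only together with a further condition, such as bilirubin, symptoms or a multiple of baseline. A stand-alone flag would create a criterion that the plan's source does not give.

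The best argument against the point itself is SAP 10.3.1. If percentages were computed within age category, with a break at 1 year, infants would not dilute the older children's figures. That partly stands, because the SAP is ambiguous. However, SAP 10.3.2 is the more specific rule and does not mention age. The base in SAP 10.3.1 also does not remove children without a criterion; it leaves them in their own rows with a denominator and no possible numerator at early visits.

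It is also fair that 38 is an efficacy number rather than a safety-set count, and that the age minimum is not said to apply within the adjunctive group. The sizes above are therefore illustrations.

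**Conclusion.** The point holds for the PCS percentages of ALT and creatinine below 1 year and of total protein below 2 months. The denominator rule and the criteria table do not fit together, and no other section removes the affected children from Nobs. The bias is downward and largest in the First Period and early analysis visits. With 10 of 38 adjunctive children under 1 year and all measured, 5.3% is printed where 7.1% applies to the children who could be classified. The true infant share is unknown before enrolment is complete, and the size moves with it. Detection of infant safety signals and the primary efficacy analysis are not affected. This is a modest correction to a descriptive table, worth making because it is cheap.

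**What to change.** In SAP 10.3.2:

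1. Define Nobs as subjects with at least one measurement, in the visit or period tabulated, at an age for which Table 12-1 or Table 12-2 gives a criterion.
2. Show beside it the number of subjects measured without an applicable criterion.
3. Apply the same rule to the PCS shift tables and add a category for no criterion at baseline, so that a value crossing an age limit is not read as a new abnormality.
4. Reconcile this with the at-risk, per-age-category base in SAP 10.3.1, so that one denominator applies to each table.

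Do not add an ALT threshold for infants.

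The cost is a few sentences of SAP text and minor programming. No new data are needed and trial conduct does not change. The percentages for the affected parameters become slightly less favourable.

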10.3.3 Listings

A subject data listing Hematology Laboratory Results presents for subjects on adjunctive therapy and for subjects on monotherapy, separately:

- Age Category
- Region/Country/Site/Subject Number
- Gender/Age/Race/Weight
- Laboratory Function Panel
- Variable
- Normal Range
- Analysis Visit
- Lab Not Done
- Date Sample Taken/Relative Day
- Fasting?
- Result / Flag
- Change from Baseline / Flag
- Abnormal

The column “Abnormal” represents the PCS criterion that is met, if applicable.

The subject data listing is repeated for:

- Blood Chemistry Laboratory Values.

A listing of Subjects with Potential Drug-Induced Liver Injury presents for subjects on adjunctive therapy and for subjects on monotherapy, separately:

- Age Category
- Region/Country/Site/Subject Number
- Gender/Age/Weight
- Analysis Visit
- ALT value
- AST value
- Bilirubin value

Note: Potential Drug-Induced Liver Injury criteria presented are:
(ALT >3 x ULN or AST >3 x ULN) and Bilirubin >2 x ULN, and
(ALT >5 x ULN or AST >5 x ULN), where ULN=Upper Limit of Normal Range

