6.3.1 Potential drug-induced liver injury IMP discontinuation criteria

Subjects with potential drug-induced liver injury (PDILI) must be assessed to determine if IMP must be discontinued. In addition, all concomitant medications and herbal supplements that are not medically necessary should also be discontinued.

The PDILI criteria below require immediate and permanent discontinuation of IMP:

- Subjects with either of the following:
 - ALT or AST ≥ 5 xULN
 - ALT or AST ≥ 3 xULN and coexisting total bilirubin ≥ 2 xULN

The PDILI criterion below requires immediate discontinuation of IMP:

- Subjects with ALT or AST ≥ 3 xULN who exhibit temporally associated symptoms of hepatitis or hypersensitivity. Hepatitis symptoms include fatigue, nausea, vomiting, right upper quadrant pain or tenderness. Hypersensitivity symptoms include fever (without clear alternative cause), rash, or eosinophilia (ie, $>5\%$).

The PDILI criterion below allows for subjects to continue on IMP at the discretion of the investigator.

- Subjects with ALT or AST $\geq 3 \times \text{ULN}$ (and $\geq 2 \times$ baseline) and $< 5 \times \text{ULN}$, total bilirubin $< 2 \times \text{ULN}$, and no eosinophilia (ie, $\leq 5\%$), with no fever, rash, or symptoms of hepatitis (eg, fatigue, nausea, vomiting, right upper quadrant pain or tenderness).

Evaluation of PDILI must be initiated as described in Section 11.2.1. If subjects are unable to comply with the applicable monitoring schedule, IMP must be discontinued immediately.

Investigators should attempt to obtain information on subjects in the case of IMP discontinuation to complete the final evaluation. Subjects with PDILI should not be withdrawn from the study until investigation and monitoring are complete. All results of these evaluations and observations, as well as the reason(s) for IMP discontinuation and subject withdrawal (if applicable), must be recorded in the source documents. The CRF must document the primary reason for IMP discontinuation.

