10.3 Clinical Laboratory Evaluations

All laboratory data summaries will be presented by analysis visit.

Shifts from baseline to end of treatment based on the normal range (ie, low, normal, high, and missing) for each hematology and clinical chemistry lab parameter will be presented.

The number and percentage of subjects with possibly clinically significant treatment-emergent laboratory values (hematology and clinical chemistry) as defined in [Section 12.3.1](#) and [Section 12.3.2](#), respectively, will be summarized. Possibly clinically significant treatment-emergent laboratory values are those that are observed during the defined treatment period at scheduled or unscheduled visits and were not observed at any visit during the Baseline period. A

subject number table will be presented for subjects with laboratory assessments meeting the marked abnormality criteria.

Individual subject data listings present laboratory data including change from Baseline and flags for abnormal and PCS values.

Subjects who meet one or more of the criteria presented in [Appendix 12.3.3](#) for potential drug-induced liver injury (PDILI) at any time-point (from both scheduled and unscheduled visits) will be listed. The listing will display only visits for which at least one of the above criteria was fulfilled for a given subject, and will display all results obtained at that visit for the specified variables. Potential Hy's law cases will be flagged. If applicable, a summary of subjects who met the criteria for PDILI will be presented separately from all relevant data collected.

PDILI laboratory results and additional PDILI information will be listed. If specific PDILI information collected separately is matching to the entries in the standard eCRF pages collected for all subjects, the specific PDILI information will be added to the corresponding listing for the standard eCRF information (eg, lifestyle information is collected for all study subjects, the additional PDILI information for alcohol and illicit drug use will be included in the listings for lifestyle). For information collected on top (eg, family history of PDILI) a new listing will be generated.

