12.3.3 Required Investigations and follow up for PDILI

Laboratory value		Symptoms ^a of hepatitis or hypersensitivity	Immediate		Follow up	
ALT or AST	Total bilirubin		Consultation requirements	Actions	Testing	Evaluation
≥3xULN	≥2xULN ^b	NA	Hepatology consult. ^c Medical Monitor must be notified within 24 hours (eg, by laboratory alert) and subject discussed with Medical Monitor ASAP.	Immediate, permanent IMP discontinuation.	Essential: Must have repeat liver chemistry values and additional testing completed ASAP (see Section 11.2.1.3); recommended to occur at the site with HCP.	Monitoring of liver chemistry values at least twice per week until values normalize, stabilize, or return to within baseline values. ^d
≥8xULN	NA	NA		Immediate, temporary or permanent, IMP discontinuation.		
≥3xULN	NA	Yes				
≥3xULN (and ≥2x baseline) and <5xULN	<2xULN	No	Discussion with Medical Monitor required if the criterion that allows for IMP continuation is met.	Further investigation – immediate IMP discontinuation not required (see Section 11.2.1.2).	Not required unless otherwise medically indicated (at discretion of investigator).	

This document cannot be used to support any marketing application and any extensions or variations thereof.

Laboratory value		Symptoms ^a of hepatitis or hypersensitivity	Immediate		Follow up	
ALT or AST	Total bilirubin		Consultation requirements	Actions	Testing	Evaluation

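### The SAP's two PDILI outputs do not deliver the listing promised in SAP 10.3: ALT/AST of 3x to <5xULN with bilirubin <2xULN is in neither, and boundary values differ between them

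*SAP*

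**What the plan says.** SAP 10.3 sets the scope of the listing. "Subjects who meet one or more of the criteria presented in" Appendix 12.3.3 "at any time-point (from both scheduled and unscheduled visits) will be listed". It adds that "The listing will display only visits for which at least one of the above criteria was fulfilled for a given subject", and that potential Hy's Law cases will carry a flag. For a summary, it commits only to one if applicable.

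Appendix 12.3.3 repeats Protocol Table 11-2. It has five rows, including ALT or AST ≥3xULN with symptoms at any bilirubin, and an asymptomatic row at "≥3xULN (and ≥2x baseline) and <5xULN" with bilirubin <2xULN.

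The output specifications are narrower:

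- SAP 10.3.2: "A table Potential Drug Induced Liver Injury (PDILI) Data presents for subjects on adjunctive therapy and for subjects on monotherapy, separately", counts for two criteria: ALT or AST ≥5xULN, and ALT or AST ≥3xULN with total bilirubin ≥2xULN.
- SAP 10.3.3: a note under the PDILI listing gives its criteria as "ALT >3 x ULN or AST >3 x ULN) and Bilirubin >2 x ULN", and ALT or AST above 5xULN. The laboratory columns are ALT, AST and bilirubin. There is no ALP, baseline ratio, symptom or Hy's Law flag column.

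Protocol 6.3.1 requires immediate discontinuation of study drug for subjects with ALT or AST ≥3xULN "who exhibit temporally associated symptoms of hepatitis or hypersensitivity".

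**The concern.** The general section and the programming specifications describe different sets of subjects. A programmer will follow the note in 10.3.3 and the two bullets in 10.3.2, because those are the concrete rules. A child could then stop drug under Protocol 6.3.1 for a symptomatic transaminase rise and still be absent from the listing meant to identify PDILI subjects.

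The listing should also support the table's count. With strict inequalities in one and ≥ in the other, it may not. The listing as specified also gives no means of showing the promised Hy's Law flag or checking it, since Protocol 11.1.1.3 makes that definition depend on ALP not reaching 2xULN.

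**Working it through.** The plan states no figure to reproduce here, so the check sets the rules side by side.

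**Notation.** *a* = ALT or AST in multiples of ULN; *b* = total bilirubin in multiples of ULN; *s* = symptoms of hepatitis or hypersensitivity; *r* = ratio to baseline.

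**Appendix 12.3.3 rows**

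1. *a* ≥ 3 and *b* ≥ 2
2. *a* ≥ 8
3. *a* ≥ 3 and *s* present
4. 3 ≤ *a* < 5, *r* ≥ 2, *b* < 2, *s* absent
5. 5 ≤ *a* < 8, *r* ≥ 2, *b* < 2, *s* absent

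**Outputs**

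- Table (10.3.2): *a* ≥ 5, or (*a* ≥ 3 and *b* ≥ 2)
- Listing (10.3.3): *a* > 5, or (*a* > 3 and *b* > 2)

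**Cases**, taking *r* = 3 (an assumption, so that the ≥2x baseline condition is met):

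| ALT/AST (xULN) | Bilirubin (xULN) | Symptoms | Appendix rows met | Table | Listing |
|---|---|---|---|---|---|
| 3, 4 or 4.99 | 1 | yes | 3 | no | no |
| 3, 4 or 4.99 | 1 | no | 4 | no | no |
| 4 | 2 | no | 1 | yes | no |
| 4 | 2.5 | yes | 1, 3 | yes | yes |
| 5 | 1 | no | 5 | yes | no |
| 6 | 1 | no | 5 | yes | yes |
| 8 | 1 | no | 2 | yes | yes |

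Rows 1, 2 and 5 are fully covered by the table, and by the listing except at exact cut-offs. Rows 3 and 4 have no criterion of their own. They reach the outputs only when ALT/AST is high enough, or (row 3) bilirubin is raised. The gap is therefore 3 ≤ *a* < 5 with *b* < 2.

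**Would substituting the Appendix rows work?** Exclusion criterion 18 starts at 3xULN, so it does not bar a baseline ALT of 2.9xULN. Suppose ALT later reaches 5.5xULN with bilirubin <2xULN and no symptoms. Then *r* = 5.5 / 2.9 = 1.9, below 2, so row 5 fails and no other row applies. Both current outputs capture this child (5.5 > 5), who also meets the ≥5xULN criterion in Protocol 6.3.1. Substitution would remove the child.

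**Would adding criteria work?** Keeping the two criteria with ≥ covers rows 1, 2 and 5. Adding rows 3 and 4 completes the Appendix set and drops nobody.

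**Weight of one case.** 1/38 = 2.6% of planned adjunctive subjects; 1/10 = 10% of planned monotherapy subjects.

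**The case against.** The strongest reply is that nothing disappears from the study report. Protocol 11.2.1 requires every PDILI event to be reported as an adverse event, so it enters the AE summaries and the listing of all AEs. ALT, AST and ALP values all appear in the chemistry listing, so Hy's Law status on ALP can be checked there. AST above 180 U/L at these ages, and ALT above 90 U/L from 1 year of age, are picked up as possibly clinically significant values. SAP 10.3 also promises listings of additional PDILI information.

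This largely stands. A reader might infer that liver signals would be understated across the report; the documents do not support that. What remains is that these other outputs do not identify PDILI cases as such. SAP Table 12-2 has no ALT threshold below 1 year, and 10.3.3 specifies no listing of additional PDILI information. The outputs for AEs leading to discontinuation are only a partial backstop: SAP 10.2.1.3 requires both permanent withdrawal and dropout, whereas the Appendix action shown for this part of the table is "Immediate, temporary or permanent, IMP discontinuation".

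A second reply is that the table's two criteria are exactly those for which Protocol 6.3.1 requires permanent discontinuation, and that row 4 permits continuation. That is a defensible basis for a count table. It does not excuse the listing, for which SAP 10.3 promises the whole Appendix set.

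A third reply is that 10.3 governs. It may be meant to, but the explicit note in 10.3.3 says otherwise, so the text needs correcting either way.

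**Conclusion.** The PDILI outputs are incomplete against SAP 10.3 and inconsistent with each other. Two of five Appendix rows have no counterpart, and exact cut-off values are treated differently in the table and the listing. The omission matters most for row 3, a discontinuation criterion in Protocol 6.3.1.

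Two limits apply. It is tempting to say that any child with ALT of 3x to 5xULN and symptoms is missed. That is true only when bilirubin is below 2xULN; at 4xULN with bilirubin 2.5xULN the child is in both outputs. The boundary mismatch bites only at exact equality.

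The documents give no expected number of cases, and it is probably small. These outputs are descriptive and no efficacy conclusion depends on them. The conclusion assumes that programming follows the criteria written in 10.3.2 and 10.3.3.

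**What to change.** For reporting only:

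- **Listing (SAP 10.3.3):** keep the two existing criteria but write them with ≥. Add ALT or AST ≥3xULN with symptoms, and ALT or AST ≥3x to <5xULN with ≥2x baseline, as in Appendix 12.3.3. Add columns for ALP, ratio to baseline, symptoms where recorded, and the Hy's Law flag.
- **Table (SAP 10.3.2):** keep both criteria and add the symptomatic one.
- **Do not** replace the ≥5xULN criterion with the Appendix rows, because subjects at 5x to <8xULN but below 2x baseline would drop out.

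The cost is SAP wording plus one table and one listing specification. ALT, AST, ALP and bilirubin are routine chemistry. Symptom data are less certain: Protocol 11.2.1.3 asks for the additional PDILI information where drug causation is reasonably possible, and for row 4 further testing is left to the investigator unless medically indicated. Some symptom entries may therefore be blank and should be shown as such.

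Separately, Protocol 6.3.1 treats ALT or AST ≥5xULN as requiring immediate, permanent discontinuation, whereas Table 11-2 and Appendix 12.3.3 treat 5x to <8xULN (with ≥2x baseline, bilirubin <2xULN and no symptoms) as conditional on monitoring. The sponsor must reconcile these passages; this review does not say which should stand.
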